8 INDEPENDENT DATA MONITORING COMMITTEE

An Independent Data Monitoring Committee (IDMC) will be formed to review data from the clinical investigation to evaluate the safety and efficacy of the investigational device. The IDMC will be formed prior to subject enrollment and the names, affiliations, and academic backgrounds of all members will be provided to the Regulatory/Competent Authority.

The members of the IDMC are responsible for safeguarding the interests of study participants, assessing the safety and efficacy of study procedures, and reviewing the overall conduct of the clinical investigation. The IDMC will review clinical investigation data to evaluate study conduct, investigational device safety, and scientific validity and integrity of the investigation.

The IDMC will provide recommendations regarding the implementation and progress of clinical investigation, including continuation, suspension and/or termination of the clinical investigation. A separate charter for the IDMC will define and describe:

- Roles and responsibilities;
- Membership;

- Frequency of meetings; and
- Documentation and reporting.

A separate CEC (Clinical Events Committee) will be formed to review all SAEs and corresponding data for each SAE. The CEC will be formed prior to subject enrollment and the names, affiliations, and academic backgrounds of all members will be provided to the Regulatory Authority.

The members of the CEC will be responsible for reviewing and adjudicating SAEs for relatedness to the hemostatic device and expectedness. A separate charter for the CEC will define and describe:

- Roles and responsibilities;
- Membership;
- Frequency of meetings;
- Adjudication process; and
- Documentation and reporting.

9 DATA COLLECTION

9.1 Completion of Case Report Forms

Prior to the start of the clinical investigation, the Sponsor representative will provide the Principal Investigator and designated investigational site staff with training on electronic CRF completion procedures. The Principal Investigator will be responsible for the timing, accuracy, and completeness of CRFs for each individual subject. The personal data recorded on all paper and electronic documents will be regarded as confidential.

The Principal Investigator will maintain a separate list of all subjects entered into the clinical investigation showing each subject's name, date of birth, and assigned subject number (for identification purposes). A Subject Identification Log will also be provided in the Investigation Site File to record the subject's initials and assigned subject number.

9.2 Source Documentation

Source documents are where clinical investigation information for subjects are first recorded. Data collected for the clinical investigation must be supported by source documents, and may include, but is not limited to, subject medical records, hospital charts, operative reports, laboratory and diagnostic test reports, and study worksheets.

9.3 Retention of Clinical Investigation Documentation

Clinical investigation records will be stored in a confidential manner so as to protect the confidentiality of subject information. All records related to this clinical investigation will be retained in appropriate investigation files.

The Principal Investigator is responsible for retaining all copies of the records for a period of no less than 5 years from the latter of the two dates: the date on which the clinical investigation is completed/terminated or the date that records are no longer required for the purposes of supporting a marketing application. In all cases, the Principal Investigator must contact the Sponsor prior to disposing of any records related to the clinical investigation. Included in records to be maintained are the signed Clinical Investigational Plan, copies of the Case Report Forms, signed consent forms, IRB approval

letters, product accountability records, correspondence concerning the clinical, and any other documents to identify the subjects.

The Sponsor must approve the destruction of any investigational records.

In addition, if the Principal Investigator moves/retires, etc., he/she should provide the Sponsor with the name and address of the person who will look after and be responsible for the clinical investigation related records.

9.4 Training

Principal Investigators and investigational site staff will be trained on the clinical investigation and the specific tasks to which they are delegated. Investigational site staff will also have documented training on applicable regulations and guidances, including Good Clinical Practice.

Further, investigators (Principal Investigators and sub-investigators responsible for enrolling study subjects and applying the investigational and control devices) will have training on use of the investigational device, control device, and the SBSS. Investigator training procedures and requirements are detailed within the Investigator Training Plan (Appendix D).

10 TERMINATION OF THE CLINICAL INVESTIGATION

10.1 Subject Withdrawals and Discontinuation

During the course of this clinical investigation, subjects will be or may elect to withdraw from investigation participation for any of the following reasons:

- Subject's withdrawal of consent;
- Any unexpected adverse device effect which is, in the opinion of the Principal Investigator, related to the device and will endanger the well-being of the subject if the treatment is continued;
- The development of any undercurrent illness(es), infection(s) or condition(s) that might interfere with the Clinical Investigational Plan; or
- Any problem deemed by the Principal Investigator and/or Sponsor to be sufficient to cause discontinuation.

All subjects discontinued from the clinical investigation due to an UADE, directly related to the clinical investigation, will be treated until the effect resolves. The Principal Investigator will clearly document the date and reason(s) for subject withdrawal in Discontinuation CRF.

Subjects who are withdrawn will not be replaced if they have received the investigational or control device. If possible, any procedures or assessments planned for the subject on withdrawal from the clinical investigation should be performed when intention to withdraw the subject is announced.

Subjects who are withdrawn prior to receiving investigational or control device will be replaced.

10.2 Early Termination of the Clinical Investigation

Both the Sponsor and Principal Investigator reserve the right to terminate the clinical investigation at any time. Should this be necessary, the procedures will be arranged on an individual site basis after review

and consultation by both parties. In terminating the clinical investigation, the Sponsor and the Principal Investigator will assure that adequate consideration is given to the protection of the subjects' interests.

11 DATA MANAGEMENT

All data will be housed in a validated database program. All data queries will be resolved with the assistance of monitoring and investigational site staff.

On resolution of all data queries, the database will be closed and data listings, summary tables, graphical output and descriptive statistics produced. All data listings, except SAEs (the final report will include the CEC adjudications for all SAEs), for inclusion into the final report, will be subject to sample quality control checks against the Case Report Forms.

Once all the subject data has been collected, the analysis and reporting will be conducted. Any data existing for subjects who have not received treatment, will not be used in the analysis. Details of these subjects will, however, be referenced in the final report.

Any data existing for subjects who have received the investigational or control device, who withdraw voluntarily or who are withdrawn from the clinical investigation, will be used in the final analysis. The inclusion of partial data will be documented in the final report. The final report will be the responsibility of Biom'Up.

12 STATISTICS

12.1 Overview

12.1.1 Primary Efficacy Endpoint

The primary efficacy endpoint of this clinical investigation is non-inferiority of HEMOBLAST™ relative to G+T for success at achieving hemostasis within 6 minutes. The definition of the primary endpoint is provided in Table 7.

12.1.2 Secondary Efficacy Endpoints

Pre-defined secondary efficacy endpoints and hypotheses that will be assessed at study completion will be:

1. Superiority of HEMOBLAST™ relative to G+T in mean preparation time from the opening of package to product being ready to use;
2. Non-inferiority of HEMOBLAST™ relative to G+T for success at achieving hemostasis within 3 minutes;
3. Superiority of HEMOBLAST™ relative to G+T for success at achieving hemostasis within 6 minutes; and
4. Superiority of HEMOBLAST™ relative to G+T for success at achieving hemostasis within 3 minutes.

The definitions of each secondary endpoint are listed in Table 8.

Table 8: Primary and secondary endpoints and hypotheses

Endpoint and Hypothesis	Definition of Endpoint
Primary Efficacy Endpoint and Hypothesis	
Non-inferiority for TTH within 6 minutes	Binary indicator of patient achieving hemostasis within 6 minutes. Time-to-hemostasis is defined as the interval from the application of study intervention until investigator deemed hemostasis. Hemostasis will be assessed via the SBSS. For the primary endpoint, a subject will be considered a success if complete hemostasis (SBSS of 0) is achieved and maintained within 6 minutes without the use of an additional hemostatic product or surgical rescue.
Secondary Endpoints and Hypotheses	
Superiority for Preparation Time	Mean preparation time, defined as the average time from the opening of package to product being ready to use (measured in minutes and seconds).
Non-inferiority for TTH within 3 minutes	Binary indicator of subject achieving hemostasis within 3 minutes. Time-to-hemostasis is defined as the interval from the application of study intervention until investigator deemed hemostasis. For this secondary endpoint, a subject will be considered a success if complete hemostasis (SBSS of 0) is achieved and maintained within 3 minutes without the use of an additional hemostatic product or surgical rescue.
Superiority for TTH within 6 minutes	Binary indicator of subject achieving hemostasis within 6 minutes. Time-to-hemostasis is defined as the interval from the application of study intervention until investigator deemed hemostasis. For this secondary endpoint, a subject will be considered a success if complete hemostasis (SBSS of 0) is achieved and maintained within 6 minutes without the use of an additional hemostatic product or surgical rescue.
Superiority for TTH within 3 minutes	Binary indicator of subject achieving hemostasis within 3 minutes. Time-to-hemostasis is defined as the interval from the application of study intervention until investigator deemed hemostasis. For this secondary endpoint, a subject will be considered a success if complete hemostasis (SBSS of 0) is achieved and maintained within 3 minutes without the use of an additional hemostatic product or surgical rescue.

12.1.3 Safety Outcomes

Endpoints used to characterize the safety profile include the rate of occurrence of all AEs and SAEs, reoperation rate due to bleeding, mean volume of intraoperative transfusions, total operative time, mean duration of hospitalization, intraoperative blood product administration, and post-operative blood product administration.

12.1.4 Individual Subject and Overall Study Success

Individual subject success will be defined as hemostasis of the target bleeding site within 6 minutes of hemostat application. The proportion of subjects, overall, and in each surgical indication, meeting this success criterion will be estimated and a 95% confidence interval for the true proportion of subjects meeting the success criteria will be presented.

Overall study success will be defined as non-inferiority of HEMOBLAST™ relative to G+T in the proportion of subjects achieving hemostasis within 6 minutes of hemostat application.

12.2 General Analysis Considerations

All statistical analyses will be performed using SAS® and R. Unless otherwise specified, all continuous endpoints will be summarized using descriptive statistics, which will include the number of subjects (n), mean, standard deviation, median, minimum, and maximum. All categorical endpoints will be summarized using frequencies and percentages.

12.2.1 Analysis Populations

Safety analyses will be performed on the Full Analysis Population, defined as all subjects who were randomized into the study and received study intervention and all lead-in subjects. Efficacy analyses will be conducted on the time to hemostasis (TTH) Analysis Population, defined as all subjects who were randomized, received study intervention, and had a TTH assessment recorded regardless of whether the measurement was censored (defined as the use of an additional hemostatic product or surgical rescue prior to the end of observation time, or failing to achieve and maintain complete hemostasis prior to the end of observation time). Data summaries will be based on the intervention received, regardless of which intervention was randomly assigned.

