3. Blot excess blood from the target bleeding site with gauze/pad or suction so the hemostatic implant material may be applied directly to the source of bleeding. The wound surface should be as dry as possible before application.
4. Apply hemostatic implant material to the source of bleeding by squeezing the bellows. Enough implant material should be applied to cover the entire source of bleeding.
5. Immediately use a wet laparotomy pad to hold the hemostatic material at the target bleeding site using wound appropriate pressure to conform the powder to the source of bleeding.
6. Maintain the hemostatic material at the target bleeding for approximately three minutes. Gently lift the laparotomy pad and inspect the area.
7. If hemostasis has not been achieved, repeat steps 3-6 or use an alternate method of hemostasis treatment.
8. Discard any unused product after opening.

HEMOBLAST™ contraindications include:

- Do not inject directly into the blood vessels.
- Do not apply HEMOBLAST™ Bellows in the absence of active blood flow, e.g., while the vessel is clamped or bypassed. Extensive intravascular clotting and even death may result.
- Do not use HEMOBLAST™ Bellows for treatment of severe or brisk bleeding.
- Do not administer to patients with known allergies or hypersensitivity to materials of porcine or bovine origin.
- To avoid risk of allergic-anaphylactoid reaction and/or thromboembolic events, which may be life-threatening, do not inject HEMOBLAST™ Bellows into a vessel or tissue.
- Do not use in the closure of skin incisions because it may interfere with the healing of the skin edges due to mechanical interposition of the powder.

After randomization, G+T will be applied to the TBS per the Instructions for Use for subjects assigned to this treatment group.

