6.4.3 Bleeding Severity and Hemostasis Evaluations

Bleeding severity and hemostasis will be assessed using the SBSS.

An SBSS score will be assigned at the following time points until hemostasis is achieved:

- Baseline – when evaluating intraoperative eligibility;
- 3 minutes;
- 6 minutes; and
- 10 minutes.

An SBSS score of 0 is equivalent to hemostasis. All other SBSS scores are considered failure of hemostasis. See below in Table 6.

Table 6. Bleeding Severity and Hemostasis

SBSS Score	0	1	2	3	4	5
Verbal Descriptor	None	Minimal	Mild	Moderate	Severe; not immediately life-threatening	Extreme; immediately life-threatening
Visual Descriptor	Dry	Oozing	Pooling	Flowing	Streaming	Gushing
Expected Intervention(s)	None	Manual pressure, cautery, adjuvant hemostat(s)	Manual pressure, cautery, suture, adjuvant hemostat(s)	Manual pressure, cautery, suture, adjuvant hemostat(s)	Manual pressure, cautery, suture, staples, tissue repair	Manual pressure, cautery, suture, staples, tissue repair
Maximum Expected ACS-ATLS Shock Risk Class	1	1	1	2	3	4
Hemostasis	Yes	No	No	No	No	No

In cases where the target bleeding site is still bleeding at the 3 minute or 6 minute assessment time points, repeat application of the randomized hemostat will be performed.

In cases where hemostasis is not achieved by 10 minutes, the Investigator may use whatever means necessary in order to control bleeding, except for any hemostatic products containing thrombin or aprotinin (Thrombin-JMI, Evithrom, Floseal, Tisseel, Evicel, Tachosil, Evarrest). Recothrom should not be used in subjects randomized to receive HEMOBLAST™, but may be used in subjects randomized to the G+T arm.

In any case where hemostasis is initially achieved but bleeding recurs prior to subject closure, the event will be documented and treated as an adverse event, and the time of observation of the re-bleed will be recorded.

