12.2.2 Handling of Missing Data

In primary analyses, missing TTH values will not be imputed. All values right censored prior to 6 minutes will be considered treatment failures for the purpose of the primary analysis. Further sensitivity analyses for the impact of potential missing data will be defined in the Statistical Analysis Plan (SAP).

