12.2.3 Subgroup Analyses

Descriptive analyses of safety and efficacy data will be presented by surgery type. The primary efficacy endpoint, as well as all secondary efficacy endpoints and safety outcomes will be presented by surgery type. Estimates of the distribution of TTH over a maximum follow-up of 10 minutes will be computed using the Kaplan-Meier method, stratified by surgery type. Kaplan-Meier estimates for the probability of continued bleeding at all scheduled assessment times (3 minutes, 6 minutes, and 10 minutes) will be displayed on each plot along with corresponding 95% confidence intervals. Additionally, the primary efficacy endpoint, as well as all secondary efficacy endpoints and safety outcomes will be presented stratified by:

- The number of interventions (separate applications of randomized hemostat);
- Baseline SBSS score; and
- Abnormal versus normal coagulation values.

The study will recruit patients undergoing elective surgery. Based upon this and the inclusion/exclusion criteria to be implemented, it is assumed that patients with abnormal coagulation studies will not be randomized and treated. In the unlikely event that patients with abnormal coagulation studies are present, a secondary analysis of the primary endpoint considering only those subjects with normal coagulation studies will also be conducted. Further, to assess the robustness of the primary endpoint with respect to possible imbalances in the frequency of patients with abnormal studies by treatment arm, a “worst-case” sensitivity analysis assuming all randomized and treated subjects in the HEMOBLAST™ arm with abnormal studies are treatment failures for the primary endpoint (TTH greater than 6 min) while all randomized and treated subjects in the G+T arm with abnormal studies are treatment successes (TTH less than 6 min). These subgroup and sensitivity analyses will be presented along with the primary results conducted on the TTH Population defined in Section 12.2.1.

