12.3.1.2 Methods of Analysis

The primary efficacy endpoint is the difference in the probability of TTH within 6 minutes comparing HEMOBLAST™ to G+T. The lower bound of the 95% confidence interval for the difference in binomial probabilities will be used to assess comparable efficacy. The primary efficacy analysis will be conducted on data from the first identified bleeding site for each subject. The estimated difference in the probability of TTH at 6 minutes between treatment arms will be adjusted for surgical indication by weighting the stratum-specific differences in observed proportions using Cochran-Mantel-Haenszel weighting.¹⁸ The trial seeks to establish comparable efficacy based upon a non-inferiority margin of 10% for the difference in the probability of TTH within 6 minutes comparing HEMOBLAST™ to G+T (HEMOBLAST™–G+T). Letting θ denote the true difference in the probability of hemostasis at 6 minutes between HEMOBLAST™ to G+T, the trial will test the null hypothesis $H_0: \theta \leq -0.10$ vs. the alternative hypothesis $H_A: \theta > -0.10$ using a one-sided level 0.025 test. The null hypothesis of inferiority will be rejected and comparable efficacy will be established if the resulting lower bound of the 95% confidence interval for θ is greater than -0.10. Comparable efficacy will be evaluated using a group sequential testing design as described in Section 12.4 with stopping boundaries defined to ensure a maximum overall 1-sided significance level of 0.025. Following the completion of the trial, a confidence interval for the estimated difference in the probability of hemostasis at 6 minutes will be computed using the Cochran-Mantel-Haenszel estimator and asymptotic variance estimate in combination with the repeated confidence interval method.¹⁹ Estimates of the distribution of TTH over a maximum follow-up of 10 minutes will be computed based on all available assessment times (3 minutes, 6 minutes, and 10 minutes) using the Kaplan-Meier method.

Analyses of the secondary efficacy endpoints will be evaluated only once, at the end of the study, using a family-wise 2-sided significance level of 0.05. Adjustment for multiple comparisons when assessing

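### The descriptive Kaplan-Meier curves would censor subjects at early rescue, so they overstate hemostasis if any rescue comes before a later scheduled assessment

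*Protocol*

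**What the plan says.** Five parts of the plan bear on this point.

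- **Censoring.** Protocol 12.2.1, repeated in SAP 10.2, describes a censored TTH measurement as "defined as the use of an additional hemostatic product or surgical rescue prior to the end of observation time". The same parenthesis also covers subjects who do not reach and hold hemostasis by the end of observation.
- **Primary rule.** Protocol 12.2.2, repeated in SAP 9.2, states: "All values right censored prior to 6 minutes will be considered treatment failures for the purpose of the primary analysis".
- **Endpoint.** Table 8 in Protocol 12.1.2 counts a subject as a success only if complete hemostasis is "achieved and maintained within 6 minutes without the use of an additional hemostatic product or surgical rescue".
- **Kaplan-Meier output.** Protocol 12.3.1.2 (SAP 10.5.2) says: "Estimates of the distribution of TTH over a maximum follow-up of 10 minutes will be computed based on all available assessment times". Protocol 12.2.3 (SAP 10.9) adds curves stratified by surgery type, showing "Kaplan-Meier estimates for the probability of continued bleeding at all scheduled assessment times" with 95% intervals. That section opens: "Descriptive analyses of safety and efficacy data will be presented by surgery type". None of these sections has its own rule for rescued subjects.
- **Timing of other treatment.** Protocol 6.4.3 (SAP 8.1) says: "In cases where hemostasis is not achieved by 10 minutes, the Investigator may use whatever means necessary in order to control bleeding". Table 7 in Protocol 6.4.5 likewise lists rescue at the 10-minute row. However, step 7 of the HEMOBLAST application steps in Protocol 6.4.2, which follows a hold of about three minutes, reads: "If hemostasis has not been achieved, repeat steps 3-6 or use an alternate method of hemostasis treatment".

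**The concern.** Kaplan-Meier estimation assumes that a censored subject has the same later chance of the event as a subject still under observation. A subject given another product or surgical rescue is treated because bleeding continues, so that assumption fails. Removing such subjects from the risk set raises the estimated hemostasis rate among those left.

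The primary analysis is protected, because it recodes values censored before 6 minutes as failures. The curves have no equivalent rule. The phrase about values censored before 6 minutes implies that the censoring time is the time of rescue. Read together, the sections would therefore drop an early-rescued subject from the curve at that time.

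Two different 6-minute success figures could then be reported for the same subjects. If the curves are drawn by arm, the one with more early rescue would look better than its observed proportion.

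**Working it through.** **The plan's own figure.** No stated figure depends on the Kaplan-Meier analysis. The nearest is the 80.1% power.

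- Inputs from Protocol 12.4.1: 88% success in both arms, a margin of 0.10, 267:133 subjects, an interim look at 240 of 400, and boundaries of 2.373 (efficacy), 0.788 (futility) and 2.036 (final).
- SE = √[0.88 × 0.12 × (1/267 + 1/133)] = 0.0345, so the standardized difference at full size is 0.10/0.0345 = 2.90.
- With an information fraction of 240/400 = 0.6, the two-look bivariate normal calculation gives power of 80.0% if the futility boundary is followed and 81.4% if it is ignored. One-sided type I error with futility ignored is 0.0250.

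The stated power is therefore reproduced, and nothing in the calculation uses the curves.

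**Kaplan-Meier illustration.** Let p3 and p6 be the observed success proportions at 3 and 6 minutes, with rescue counted as failure. Let r be the share of subjects rescued, and so censored, between those assessments. Then

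KM success at 6 min = 1 − (1 − p3) × [1 − (p6 − p3)/(1 − p3 − r)].

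Here p6 = 0.88 is the design assumption. The documents give neither p3 nor r, so both are assumed. With p3 = 0.70:

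- r = 0: 1 − 0.30 × (1 − 0.18/0.30) = 88.0%, the observed proportion
- r = 0.02: 1 − 0.30 × (1 − 0.18/0.28) = 89.3%
- r = 0.04: 1 − 0.30 × (1 − 0.18/0.26) = 90.8%
- r = 0.06: 1 − 0.30 × (1 − 0.18/0.24) = 92.5%

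Over a range of assumed p3:

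| Early rescue r | KM success at 6 min, p3 from 0.8 to 0.5 | Overstatement, points |
|---|---|---|
| 1% | 88.4–88.8% | 0.4–0.8 |
| 2% | 88.9–89.6% | 0.9–1.6 |
| 5% | 90.7–92.2% | 2.7–4.2 |
| 10% | 96.0–97.5% | 8.0–9.5 |

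**The same in counts.** Take an arm of 267 with assumed counts of 160 successes at 3 minutes, 13 rescued between 3 and 6, and 75 further successes at 6. The observed proportion is 235/267 = 88.0%. Kaplan-Meier gives 1 − (107/267) × (1 − 75/94) = 91.9%.

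**Unequal rescue, if curves are drawn by arm.** Suppose observed success is 78% on HEMOBLAST and 88% on G+T, p3 = 0.60, and 5% are rescued early on HEMOBLAST only. The HEMOBLAST curve shows 1 − 0.40 × (1 − 0.18/0.35) = 80.6%. The observed difference of −10 points appears as −7.4.

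**Effect at 10 minutes.** Assume 88% success at 6 minutes and 93% at 10. If 2% are rescued just after the 6-minute assessment, Kaplan-Meier gives 1 − 0.12 × (1 − 0.05/0.10) = 94.0%. If rescue comes only at or after the 10-minute assessment, it gives 93.0%, and the values at 3 and 6 minutes are also unbiased.

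**The case against.** The strongest reply is that, under the planned conduct, there is no bias. The randomized hemostat is to be re-applied at 3 and 6 minutes if bleeding continues, and other means are foreseen only after 10 minutes. A subject rescued then has been followed for the whole window, and the curve equals the observed proportion at every assessment. This stands, so a reader should not infer that the curve and the primary proportion will necessarily disagree. But the plan does not rely on rescue always being late. Its endpoint definition, its censoring definition and the rule for values censored before 6 minutes all provide for earlier events, and step 7 leaves room for them.

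A reader might also infer that the curves contradict the primary rule. The documents do not support that. Protocol 12.2.2 says how censored values map to the primary endpoint and limits that mapping to the primary analysis. The result is different handling in a descriptive output.

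Third, the censoring time for the curves is inferred. The definition sits inside a population definition, and no section says outright that rescued subjects leave the risk set at rescue. That is fair, although the wording on values censored before 6 minutes points that way and no other rule is offered.

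Fourth, the sizes rest on assumed inputs. With 12% failing at 6 minutes, r = 4% means that one third of failures were rescued before the protocol foresees it, and r = 6% means half. The low end of the range is more plausible.

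Finally, readers will have the observed 6-minute proportions, overall and by indication, under Protocol 12.1.4. That limits the harm but leaves two figures to explain.

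**Conclusion.** The point holds as a conditional gap in a descriptive analysis. As written, subjects given another product or rescue before a later assessment would be censored informatively in the Kaplan-Meier curves, and any resulting bias is toward more hemostasis. At 6 minutes it is about 0.9 to 1.6 points if 2% are rescued early and 2.7 to 4.2 points if 5% are, for assumed 3-minute success of 50% to 80% and 88% at 6 minutes. It is zero if all rescue follows the 10-minute assessment. The documents give no rate from which to choose between these cases.

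The non-inferiority conclusion is not at risk. The curves have no part in the primary test, the sample size, the stopping boundaries, type I error control or the fixed sequence. This is a minor point, worth correcting because the correction is nearly free.

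**What to change.** Add a sentence to Protocol 12.3.1.2 and 12.2.3 and to SAP 10.5.2 and 10.9. It should say that, in the Kaplan-Meier analysis, subjects given another hemostatic product or surgical rescue are kept as not hemostatic through 10 minutes, with censoring at 10 minutes and not at the time of rescue.

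The same text should apply the endpoint's requirement that hemostasis be held as well as reached. Otherwise a subject who is dry at 3 minutes and then re-bleeds could be an event on the curve but a failure in the endpoint. With both parts in place and complete assessments, the curve matches the observed proportion at 3, 6 and 10 minutes. The rescue sentence alone does not guarantee this.

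The cost is a short text change and about a line of code for rescue, plus the coding of re-bleeds, whose time of observation is already to be recorded. If no rescue is early, the rescue rule changes nothing.

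Separately, step 7 of the application steps in Protocol 6.4.2 and the 10-minute provisions in Protocol 6.4.3, Table 7 and SAP 8.1 differ on when other treatment may be used. The sponsor should reconcile them.
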